**Table 4.3 Dose Modification Guidelines for Panobinostat and Ipilimumab**

Cohort	Ipilimumab Dose Panobinostat Dose	Dose Modification #1	Dose Modification #2
1	3 mg/kg	1 mg/kg	Off Study
	5 mg	5 mg	
2	3 mg/kg	3 mg/kg	Off Study
	10 mg	5 mg	
3	3 mg/kg	3 mg/kg	3 mg/kg
	15 mg	10 mg	5 mg
4	3 mg/kg	3 mg/kg	3 mg/kg
	20 mg	15 mg	10 mg
-1	1 mg/kg	Off Study	Off Study
	5 mg		

### 4.3.7 Supportive Care Guidelines

#### 4.3.7.1 Guidelines For Infusion Reactions

Ipilimumab may induce infusion or hypersensitivity reactions. These reactions may manifest with fever, chills, rigors, headache, rash, pruritus, arthralgias, hypo or hypertension, bronchospasm, or other symptoms. Infusion reactions should be graded according to Common Terminology Criteria for Adverse Events (CTCAE, Version 4.0) guidelines. The Sponsor will be responsible for the appropriate notification of Study Investigators and the DMC of  $\geq$  Grade 3 infusion reactions. Treatment recommendations and dose modification guidelines are provided below. Supportive care guidelines may be modified based on clinical judgment, local treatment standards and guidelines, and/or specific symptoms, as appropriate: For Grade 1 symptoms: Mild reactions (localized cutaneous reactions including mild pruritus, flushing, rash),

- Decrease the rate of ipilimumab infusion until recovery from symptoms.
- Remain at bedside and monitor subject until resolution of symptoms.
- Diphenhydramine 50 mg, may be administered at the discretion of the treating physician.
- When symptoms resolve, restart the infusion at the original infusion rate
- Institute additional treatment as clinically indicated.

If a subject has a Grade 1 infusion reaction with ipilimumab, prophylactic preinfusion medications should be given prior to all subsequent ipilimumab infusions. The following prophylactic preinfusion medications are recommended in this setting to administered at least 30 minutes prior to ipilimumab administration;

- diphenhydramine 50 mg (or equivalent) and/or • acetaminophen 325 to 1000 mg

For Grade 2 symptoms: Moderate reactions [ie, any symptom not listed above (mild symptoms) or below (severe symptoms) such as generalized pruritus, flushing, rash, dyspnea, hypotension with systolic blood pressure  $> 80$  mm Hg], require infusion interruption but respond promptly to symptomatic treatment [eg, antihistamines, non-steroidal anti-inflammatory drugs, narcotics, corticosteroids, i.v. fluids]; prophylactic preinfusion medications indicated for  $\leq 24$  hours.

- Discontinue the study drug infusion.
- Begin an i.v. infusion of normal saline, and treat the subject with diphenhydramine 50 mg i.v. (or equivalent) and/or acetaminophen 325 to 1000 mg. • Remain at bedside and monitor subject until resolution of symptoms. • Corticosteroid therapy may be administered at the discretion of the treating physician.
- When symptoms resolve, restart the infusion at 50% of the original infusion rate; if no further complications ensue after 30 minutes, the rate may be increased to 100% of the original infusion rate.
- Monitor subject closely. If symptoms recur, immediately discontinue the infusion; no further study drug will be administered at that visit. Administer diphenhydramine 50 mg i.v., and remain at bedside and monitor the subject until resolution of symptoms.

If a subject has a Grade 2 infusion reaction with ipilimumab, prophylactic preinfusion medications should be given prior to all subsequent ipilimumab infusions. The following prophylactic preinfusion medications are recommended in this setting to administered at least 30 minutes prior to ipilimumab administration;

- diphenhydramine 50 mg (or equivalent) and/or

- acetaminophen 325 to 1000 mg
- If considered necessary, corticosteroids (up to 25 mg of SoluCortef or equivalent) may be used.

For Grade 3 or Grade 4 symptoms: (Severe reaction [eg, bronchospasm, generalized urticaria, systolic blood pressure  $\leq$  80 mm Hg, or angioedema], Grade 3: prolonged [ie, requiring 6 or more hours to respond to symptomatic medication and/or discontinuation of infusion]; recurrence of symptoms following initial improvement; hospitalization indicated for other clinical sequelae [eg, renal impairment, pulmonary infiltrates]. Grade 4: life-threatening; pressor or ventilatory support indicated).

- Immediately discontinue the study drug infusion. No further study drug will be given
- Begin an i.v. infusion of normal saline, and treat as follows: bronchodilators, epinephrine 0.2 to 1.0 mg of a 1:1,000 solution for subcutaneous administration or 0.1 to 0.25 mg of a 1:10,000 solution injected slowly for i.v. administration, and/or diphenhydramine 50 mg i.v. with methylprednisolone 100 mg i.v. (or equivalent), as needed.
- Remain at bedside and monitor subject until recovery from symptoms. Subject should be monitored until the Investigator is comfortable that the symptoms will not recur.
- The amount of study drug infused must be recorded on the case report form (CRF).
- In the case of late-occurring hypersensitivity symptoms (eg, appearance of a localized or generalized pruritus within 1 week after treatment), symptomatic treatment may be given (eg, oral antihistamine, or corticosteroids). In addition, Investigators should also follow their institutional guidelines for the treatment of anaphylaxis.

#### **4.3.7.2 Guidelines for Management of Gastrointestinal AEs and**

##### ***Endocrinopathies***

Immune-related adverse events are well described with the use of ipilimumab. All subjects who receive treatment on this study should be closely monitored for any signs related to gastrointestinal or endocrine systems and aggressively managed at the first onset of clinical symptoms. A high index of suspicion for immune-mediated colitis should be maintained in subjects who present with diarrhea or other abdominal symptoms. Prompt initiation of appropriate therapy, including early administration of steroids should be instituted as consistent with the guidelines on management of diarrhea within the ipilimumab program (see Appendices 5-8). Specific algorithms for the management of immune-related AEs, diarrhea, hepatotoxicity, and endocrinopathies have been developed within the ipilimumab clinical program and are provided for reference in Appendices 5-8.

#### **4.4 Blinding/Unblinding**

This is an open label study. Blinding will not be utilized.

#### **4.5 Destruction and Return of Study Drug**

##### **4.5.1 Destruction of Study Drug**

If study drug panobinostat sourced by the investigator by Novartis are to be destroyed on site, it is the investigator's responsibility to ensure that arrangements have been made for the disposal, procedures for proper disposal have been established according to applicable regulations, guidelines and institutional procedures, and appropriate records documented.

## 5 STUDY ASSESSMENTS AND PROCEDURES

### 5.1 Flow Chart/Time and Events Schedule

**Table 5.11 Screening Days -28 to -1**

Procedure	Screening Visits	Notes
Eligibility Assessment	X	
Informed Consent	X	
Eligibility Criteria	X	
History	X	
Pathology review	X	
Physical examination	X	
Vital Signs	X	
Height and Weight	X	
Performance Status	X	
ECG	X	Single 12-lead ECG or triplicate if planned to be used as baseline (Induction Cycle 1 Day 1)
Chem panel, CBC	X	
Free T4, TSH, ACTH, Cortisol	X	
Liver and HIV serologies	X	HIV, HepBsAg, Hep C ab
PT/PTT	X	
Pregnancy test	X	Serum
Urinalysis	X	
Ophthalmologic exam	X	With slit lamp as a baseline
Tumor assessment	X	CT C-A-P with contrast, and unless contraindicated, MRI brain with gadolinium
Tumor Biopsy	X	Voluntary

**Table 5.12 During Treatment, Day 1 onward**

Study Cycle	Induction Cycle						Maintenance Cycle	End of Treatment	Follow-up	Notes
Cycle #	1				2		Each Cycle			
Day of Cycle 	1	5	22	35	1	22				
Safety Assessments										
Physical exam	X 		X		X	X	X	X	X	
Ophthalmology Exam	X									Baseline only
Vital Signs	X		X		X	X	X	X	X	
Weight	X		X		X	X	X	X	X	
PS	X 		X		X	X	X	X	X	
ECG	X 	X 			X		X	X		Triplicate 12-lead for Induction Cycle 1 Day 1 & Day 5; single 12-lead ECG otherwise
Chem Panel, CBC	X 		X		X	X	X	X	X	
PT/PTT	X 									
T4, TSH	X 		X		X	X	X			
Serum Preg	X 						X			
Urinalysis	X 				X		X			
SAE Monitoring	X		X		X	X	X	X	X	
Ipilimumab	X		X		X	X				
Panobinostat	X		X		X	X	X 			
Disease Assessment					X		X	X	X	
PD Blood	X		X		X	X	X	X		
Tumor bx				X 						

 All study visits may be scheduled +/- 3 days from planned visit date.

 These tests will not be repeated on Cycle 1 Day 1 of the initial treatment period if completed for screening less than 72 hours (3 days) before the first dose of the study drugs.

 Triplicate ECGs at least 5 minutes apart will be done pre-dose on C1 D1 & C1 D5.

 Biopsy to be done between Days 35 and 42.

 Panobinostat will continue to be administered thrice weekly during the maintenance cycles.

6. Patients will continue to be followed for PFS and OS.

## 5.2 Study Materials

The Moffitt Cancer Center provide all of the required equipment for safe drug administration including all therapies as well as equipment for proper storage of study documentation, storage of clinical supplies, and processing of laboratory samples. The site will provide medications required for standard treatments. A current and fully- stocked advanced cardiac life support (ACLS) cart including resuscitation equipment and other agents to treat anaphylaxis (see Section 4.3.4) will be immediately available on the premises. The site will provide all materials required for accurate source documentation of study activities.

Case report forms (electronic or hard copy) will be provided by the Moffitt Clinical Trials Office. Novartis will provide panobinostat and ipilimumab will be from commercial stock.

### **5.3 Safety Assessments**

All subjects who receive at least one dose of panobinostat and or Ipilimumab will be evaluated for safety parameters. Additionally, any occurrence of an SAE from time of consent until 90 days post discontinuation of study drug dosing will be documented. Safety will be evaluated for all treated subjects using the NCI CTCAE version 4.0. Safety assessments will be based on medical review of AE reports and the results of vital sign measurements, physical examinations and clinical laboratory tests. The incidence of AEs will be tabulated and reviewed for potential significance and clinical importance. The schedule or required visits, tests, procedures and assessments are described in the Procedural Outline Tables. In limited instances, scheduled evaluations can occur outside of this time frame but only within the windows noted. Please see the Procedural Outline Tables for a comprehensive list of assessments/procedures (Section 5.1). If the screening evaluation (physical exam, physical measurements, ECOG status and laboratory tests) is conducted within the 72 hour window of the first dose of panobinostat, then a single evaluation for these assessments may count for screening and pre-dose evaluation. If a subject has a delay in study drug administration for any reason, then assessments, laboratory tests and scans will be correspondingly delayed.

A screening 12-lead ECG will be performed to assess study eligibility. Additional 12-lead ECGs will be performed at a minimum at scheduled time points as indicated in Table 5.12. For all patients, a minimum of 3 sequential 12-lead ECGs, separated by at least 5 minutes, must be performed on cycle 1 day 1 prior to the first administration of oral panobinostat or within 72 hours prior to that day in order to get an accurate baseline QTcF calculation. Additionally, triplicate ECGs will be performed on cycle 1 day 5. The recommended dose modifications due to QTc interval prolongation are outlined in section 4.3.6.

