- **Safety Outcome Measures:** All subjects who receive study drug therapy will be evaluated for safety. Safety assessments will be based on medical review of adverse event reports and the results of vital sign measurements, physical examinations, and clinical laboratory tests. Triplicate 12-lead electrocardiograms (ECGs) will be collected prior to dosing on Day 1 of induction cycle 1. Single 12-lead ECGs will be collected at screening, prior to dosing on Day 1 of all treatment cycles (with the exception of induction cycle 1 as above) and at the end of treatment.

Adverse events will be categorized using the most current version of MedDRA and adverse events and laboratory tests will be graded using National Cancer Institute (NCI) Common Terminology Criteria for Adverse Events (CTCAE) v4.0. Hepatic adverse events (AST, ALT, T Bili) will also be recorded relative to ULN. Immune-related adverse experiences (irAEs) among treated subjects will be specifically assessed as well.

- **Efficacy Measures:** Tumor response will be determined for all subjects by RECIST 1.1 (see Appendix 3) as well as by immune-related response criteria (irRC; see Appendix 4). RECIST 1.1 will be used for statistical analysis of efficacy in this study. Treatment decisions related to subject management may be based on the irRC criteria, but for the purposes of reporting efficacy RECIST 1.1 criteria will be used. Assessments of tumor status will be made during screening, then at 6 weeks and 12 weeks, and subsequently every 12 weeks. Tumor assessments at the end-of-treatment (EOT) or 90-day follow-up visit will be performed only if not assessed within the prior 12 weeks. Individual subject's best overall response (BOR) will be assessed, and progression free survival (PFS) will be calculated by RECIST 1.1 response criteria. Other endpoints are Objective response (OR) defined as BOR outcome of CR or PR for RECIST 1.1, disease control (DC) defined as BOR outcome of CR, PR, or Stable Disease by RECIST 1.1. Duration of response and duration of disease control will also be calculated.

Statistical Methods:

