# **3 INVESTIGATIONAL PLAN**

## **3.1 Study Design and Duration**

This is a Phase 1 open label study of panobinostat administered in combination with ipilimumab. Subjects with unresectable Stage III or Stage IV melanoma who meet the eligibility criteria will undergo screening evaluations within 28 days prior to initiation of study therapy. The study will consist of a dose escalation assessment of the safety and tolerability of oral panobinostat administered concurrently in combination with ipilimumab. Treatment will be divided into induction with ipilimumab and panobinostat and a maintenance phase with panobinostat alone consistent with the general principles of ipilimumab therapy. It is anticipated that this evaluation will enable selection of the RP2D of this combination for further clinical testing. A study schematic is presented below:

Each treatment cycle will be 42 days (6 weeks) during the induction phase, and 84 days (12 weeks) during the maintenance phase. Panobinostat will be administered orally TIW on Days 1-42 of each 42 day treatment cycle. Ipilimumab will be administered intravenously (IV) once every 3 weeks on Days 1 and 22 of each treatment cycle. The induction phase will last for up to 2 treatment cycles. During the maintenance phase, panobinostat will be administered orally TIW on Days 1-84 of each 84 day treatment cycle. Subjects will continue maintenance panobinostat treatment with their designated combination dose regimen until progression of disease, discontinuation due to toxicity, withdrawal of consent or any other reason as specified in Section 3.4.

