**There will be no intra-subject dose escalation.** Decisions regarding dose escalation between cohorts will be guided by the incidence of drug-related dose limiting toxicities (DLTs) occurring within 84 days (12 weeks; through Day 42 of induction cycle 2) of initiation of study therapy. If three patients complete their 84 day period of treatment without DLT, then at least three additional patients must exceed 9 weeks without MTD being reached to be able to dose escalate. This DLT observation interval is based upon inclusion of the known median times to onset of common immune-related adverse events attributed to ipilimumab (see Section 4.3.5.1) and allows for a substantial amount of time for unexpected toxicities with the combined administration of panobinostat and ipilimumab to emerge. Subjects who do not complete the DLT observation period for reasons other than drug-related toxicity will be replaced. One of the following five decisions will be made at the end of the DLT period for each cohort of 3 subjects based on the number of DLT's observed:

- S: stay at the same dose and enroll a cohort of 3 more subjects at that dose
- E: escalate to the next higher dose by enrolling 3 more subjects
- D: de-escalate to the lower dose, and enroll 3 more subjects at the lower dose, or
- DU: declare the current dose as unacceptable and unsafe, de-escalate to the lower dose, and enroll 3 more subjects at the lower dose
- C: Study completed and dose is declared to be the MTD

Decisions S or E are allowed by the design if determined that the corresponding doses are safe based on the target toxicity. Decisions D or U are based on evidence of exceeding predetermined toxicity. With a target toxicity rate of 18%, allowing any dose with estimated  $P_T$  in the (17%, 19%) interval to be selected as the MTD in this study, and with a maximum fixed total of 36 subjects at the dose escalation phase in each arm, the algorithm for dose escalation decisions based on possible total number of subjects at each dose cohort is described in Table 3.2 below.

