#### **Panobinostat/Ipilimumab Dose Modification Guidelines for Non-hematologic and Hematologic Events Other Than Infusion Reactions:**

- Patients who experience hepatic non-hematologic DLT irrespective of irAE or any Grade 3 or greater irAE will be removed from study with no further dose reduction.
- For patients who experience a first episode of non-hepatic non-hematologic DLT or a first episode of hematologic DLT, therapy may be reinitiated at the next lowest panobinostat/ipilimumab dose level as specified below in Table 4.3 if the event has resolved to less than or equal to Grade 1 in severity at the time the next cycle is due.
- For patients who experience a second episode of either hematologic or non-hepatic non-hematologic DLT, a second dose reduction may be performed as specified below for the successive cycle if the second dose-limiting event is distinct in nature from the first event and the event has resolved to less than or equal to Grade 1 in severity at the time the next cycle is due.
- In the event of a DLT, successive cycles of therapy may be delayed up to 14 days pending resolution of the toxicity to grade 1 or less in severity. Patients on dose level #1 will not be dose reduced in the event of DLT. Patients on dose level #2 will be allowed a maximum of 1 dose reduction, with the second occurrence of DLT necessitating removal from study.
- Any patient who develops significant irreversible (i.e. more than 2 weeks after the last dose of study drug) organ dysfunction (i.e., Grade IV non-hepatic non-hematologic toxicity) or anaphylaxis considered to be related to study drug will also be removed from study with no further dose reduction.
- All cardiac events should be treated as per the local standard of care and referred to a specialist if clinically indicated. The readings of ECGs will use the Fridericia correction: QTcF. Any final decisions concerning dose modifications or permanently discontinuing the patient from study drug due to QTcF prolongation will be based on the

assessment of the principal investigator. If a patient cannot be dosed due to prolonged QTcF for more than 7 days since last dose, patient should be discontinued from study.

**Table 4.2** Criteria for dosing delays, dose-reductions, and re-initiation of treatment due to study drug-related QTcF abnormalities

ECGs to be performed at specified time point	Abnormality Noted	Dose Modification Guideline - At any time during a cycle of therapy (including intended day of dosing)

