**5.4 Efficacy Assessments**

In this study, immune-related Response Criteria (irRC; see Appendix 4) will be used to assess subject response to study treatment and guide clinical care. However, response- based assessments in this study will be captured using both modified irRC and RECIST 1.1. The investigator will determine the irRC response at each tumor assessment. The RECIST 1.1 response for the patient will be calculated from the tumor assessment data by the Sponsor and will be used for reporting purposes. The RECIST 1.1 criteria will be used to determine subjects’ best overall response (BOR), and for statistical analysis of efficacy in this study. Assessments of tumor status will be made during screening and then at 6 and 12 weeks and then every 12 weeks thereafter. The irRC represent modifications of the modified WHO criteria reflecting the clinical experience with ipilimumab in the completed and/or ongoing clinical studies in which objective and durable responses (as per mWHO) were observed in subjects following progression and without intervening alternative anti-cancer therapy. As such, the irRC are designed to capture clinical activity of ipilimumab immunotherapy that may not be adequately addressed by the RECIST 1.1 criteria and will only be used for patient management decisions, not formal efficacy reporting.

[REDACTED]

[REDACTED]

[REDACTED]

[REDACTED]

[REDACTED]

[REDACTED]

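### Section 5.3 moves tumor scans with every dosing delay, so recorded progression dates depend on toxicity; separately, the two statements of the DLT window disagree once a cycle slips

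*Combined protocol and SAP*

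**What the plan says.** Section 5.3 states: "If a subject has a delay in study drug administration for any reason, then assessments, laboratory tests and scans will be correspondingly delayed". It sets no limit on the delay and makes no exception for imaging.

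Section 5.4 states: "Assessments of tumor status will be made during screening and then at 6 and 12 weeks and then every 12 weeks thereafter". The synopsis gives the same weeks. Neither says whether the weeks run from first dose regardless of dosing. Table 5.12 places disease assessment by cycle (cycle 2 Day 1, then each maintenance cycle, end of treatment and follow-up) and notes: "All study visits may be scheduled +/- 3 days from planned visit date".

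Section 8.2.2.1 counts PFS from first dosing to the first observed progression or death, and duration of disease control from the start of treatment to documented progression. Section 4.3.6 says that after a DLT "successive cycles of therapy may be delayed up to 14 days pending resolution of the toxicity".

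Section 3.1 bases escalation on DLTs "occurring within 84 days (12 weeks; through Day 42 of induction cycle 2) of initiation of study therapy". The synopsis and Section 4.3.3 use the same double definition. Section 4.3.1 gives 84 days alone, and replaces subjects with missed doses or an incomplete first cycle only when the reason is not study-drug toxicity.

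**The concern.** Progression is dated by the scan that shows it. If the scan moves because drug was held, the recorded date moves for a reason unrelated to the tumor. Delays are likely to be more common where toxicity is more common, so scan timing may differ between dose levels. Section 8.3.2 plans Kaplan-Meier medians at the MTD and a possible look at dose against efficacy, and both use these dates.

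The second matter touches the primary objective. The two statements of the DLT window coincide only if no cycle is delayed. After a delay, an event between the two end dates counts on one statement and not on the other. With cohorts of 3, one event can change an escalation decision.

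**Working it through.** **1. The plan's own figure.** Section 3.1: "Each treatment cycle will be 42 days (6 weeks) during the induction phase, and 84 days (12 weeks) during the maintenance phase". So 12 × 7 = 84 and 2 × 42 = 84. The two statements of the DLT window agree exactly with no delay. With a delay of d days before cycle 2, cycle 2 Day 42 falls on day 84 + d: day 91 for d = 7 and day 98 for d = 14 (14/84 = 16.7% longer).

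**2. Scan dates.** On time: about days 42, 84, 168. Under Section 5.3 with d = 14: 42 + 14 = 56, 84 + 14 = 98, 168 + 14 = 182. Weeks 6 and 12 become weeks 8 and 14, well beyond a 3-day window.

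**3. Effect on recorded PFS.** Assumptions: exponential time to progression, progression recorded at the next scan, one 14-day delay before the first scan. The 57-day median is derived from Section 1.4.2.3, which gives about 11% progression-free at 6 months on ipilimumab 3 mg/kg: rate = −ln(0.11)/182 = 0.0121 per day, median = ln 2/rate = 57 days. The other medians are assumed. The share of subjects delayed is not in the documents, so it is varied.

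| True median (days) | Recorded later | Recorded earlier | Mean change (days) | Recorded median if 0% / 50% / 100% delayed |
|---|---|---|---|---|
| 57 | 81.8% | 18.2% | +2.6 | 84 / 84 / 98 |
| 84 | 81.3% | 18.7% | +1.6 | 84 / 98 / 98 |
| 120 | 81.5% | 18.5% | +1.0 | 168 / 168 / 182 |
| 180 | 81.8% | 18.2% | +0.6 | 252 / 252 / 182 |

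The mean moves little because the shifted scan catches some progressions sooner. Progression on days 43 to 56 is seen at day 56 instead of day 84 (28 days earlier). Progression on days 85 to 98 is seen at day 98 instead of day 168 (70 days earlier), and so on. For the 57-day median, 9.4% fall in the first such interval and 8.8% in the later ones. The mean change is 0.818 × 14 − 0.094 × 28 − 0.088 × 70 = 11.45 − 2.63 − 6.16 = 2.7 days from these rounded shares, or 2.6 unrounded.

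The median can move much more than the mean because it sits on scan dates. At a true median of 84 days it steps from 84 to 98 with only 10% of subjects delayed, a knife-edge case because the true median equals a scan date. At 180 days it falls from 252 to 182 if all are delayed. The proportion without progression at the first scan falls with delay: at the 57-day median, from 60.1% at day 42 to 50.7% at day 56.

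**4. Effect of the DLT window.** With a constant hazard and 18% risk by day 84, risk by day 84 + d is 1 − 0.82^((84+d)/84): 19.3% at day 91 and 20.7% at day 98, both outside the plan's (17%, 19%) interval. If every subject had the day-98 window, the chance of at least 2 DLTs in 3 would rise from 0.0855 to 0.1105, and of at least 3 in 6 from 0.0759 to 0.1073. These are upper bounds, since only some subjects are delayed. In Table 8.1 one extra event turns E at 0/3 into S at 1/3, E at 1/6 into S at 2/6, and S at 2/6 into DU at 3/6.

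**5. Laboratory tests.** Table 5.12 schedules chemistry and blood counts in induction on Days 1 and 22 only. From cycle 1 Day 22 to cycle 2 Day 1 is 21 days; with Section 5.3 and a 14-day delay it is 35. Section 4.3.3.1 makes Grade 3 AST/ALT dose-limiting if not back to Grade 1 or less within 5 days, and Section 4.3.3.2 makes Grade 4 neutropenia dose-limiting at 7 days or more.

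**The case against.** A reader might infer a flat contradiction between Section 5.3 and a fixed calendar. The documents do not go that far: Section 5.4 and the synopsis give weeks without saying that they ignore delays, and Table 5.12 is cycle-based, which fits Section 5.3. What stands is an unresolved time origin.

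A reader might infer that delay inflates PFS and disease control at toxic doses. The model does not show this: the mean shift is small, some subjects are recorded earlier, the recorded median can fall, and the proportion free of progression at the first scan drops. Nor does delay alone carry a subject past the 12-week stable-disease threshold in Section 8.2.2.1, because an on-time scan on day 85 also has 84 elapsed days. Efficacy is a descriptive secondary objective with no comparator, and Appendix 4 allows extra scans on suspected progression.

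A reader might blame Section 5.3 for the split DLT window. It never mentions the window; the split comes from the double definition together with cycle delay. The 14-day allowance in Section 4.3.6 applies after a DLT, when the subject is already counted, and hepatic DLTs and Grade 3 or greater irAEs lead to removal rather than delay. A second event in such a subject should not change the count. What remains is a subject delayed by drug toxicity short of a DLT, who is not replaced under Section 4.3.1.

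On laboratory tests, Section 5.3.1 lets the investigator repeat them, restart after a DLT requires resolution to Grade 1 or less, and Sections 6.1.1 and 6.2.1 require follow-up of events that interrupt drug. These soften the problem, but none sets a test schedule suited to the 5-day and 7-day definitions.

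**Conclusion.** The point holds in limited form. As written, Section 5.3 makes scan dates depend on toxicity and tolerability while time-to-event endpoints run from first dose. For one 14-day delay the individual error is usually 14 days later and sometimes 28 or 70 days earlier. The mean change is 0.6 to 2.6 days across true medians of 180 to 57 days, and the recorded median may step by a whole scan interval or not at all. The direction of any bias across dose levels is not established. These sizes rest on exponential progression and a single delay before cycle 2.

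The DLT-window ambiguity is a separate defect. It equals the length of the cycle delay and matters for evaluable subjects delayed by sub-DLT drug toxicity. The documents do not say how many there would be or cap such delays, so 14 days is an illustration. It deserves correction because it can reach the escalation count.

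**What to change.** Scans: delete them from the Section 5.3 sentence, and make clear that the assessments it defers do not include tumor assessments. State in Section 5.4 and the synopsis that tumor assessments occur at weeks 6 and 12 from first dose and every 12 weeks thereafter, regardless of dosing delays. Align the disease-assessment row of Table 5.12. The number of scheduled time points is unchanged. The cost is wording, plus some delayed subjects whose scan no longer coincides with an infusion visit.

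DLT window: reconcile the synopsis and Sections 3.1, 4.3.1 and 4.3.3, and state which expression governs after a cycle delay. The choice belongs to the sponsor and investigators.

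Laboratory tests: reconcile the deferral in Section 5.3 with the duration-based DLT definitions in Sections 4.3.3.1 and 4.3.3.2. Any cost in visits or blood draws depends on how that is resolved.
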